5.7.1. Primary Endpoints

5.7.1.1. Definition of Estimand

For the primary objective of evaluating the efficacy of vutrisiran compared with placebo on the composite outcome of all-cause mortality and recurrent CV events, the estimand is defined as follows:

- **Target patient population:**
 - **Overall population:** Patients with hATTR or wtATTR amyloidosis with cardiomyopathy regardless of use of tafamidis.
 - **Vutrisiran monotherapy subgroup:** Patients with hATTR or wtATTR amyloidosis with cardiomyopathy who are tafamidis naïve.
- **Treatment condition:**
 - **Overall population:** Vutrisiran or placebo administered as a subcutaneous injection 25mg q3M (once every 12 weeks) with or without concomitant use of tafamidis.
 - **Vutrisiran monotherapy subgroup:** Vutrisiran or placebo administered as a subcutaneous injection 25mg q3M (once every 12 weeks) without concomitant use of tafamidis.
- **Endpoint:** Composite endpoint of all-cause mortality and recurrent CV events (CV hospitalizations and urgent HF visits).
- **Population-level summary:** Hazard ratio (HR) for the composite outcome between the vutrisiran and placebo arms.
- **Intercurrent events (ICE) strategies:** Intercurrent events include treatment and study discontinuation, tafamidis drop-in (applicable to vutrisiran monotherapy subgroup only), selected prohibited medications, **CCI**, heart transplantation and LVAD placement, and events due to COVID-19, etc. They require different handling strategies, which are described in [Table 6](#) below.

Table 6: Intercurrent Event Strategies for the Primary Analysis of Primary Endpoints

Intercurrent Event	Primary analysis of composite endpoint Strategy with Rationale
Treatment and study discontinuation	
Following treatment discontinuation, patients may opt to remain on the study for CV events data collection. Patients who discontinue study will no longer report CV events but will be followed up for vital status. In the CCI [REDACTED], the follow-up duration needs to be the same for CV events and deaths, therefore deaths collected after study discontinuation will be excluded from the CCI [REDACTED] but will be included in the component analysis of all-cause mortality.
 
Treatment policy strategy in the component analysis of all-cause mortality: all deaths collected will be included in the analysis, including deaths after treatment and study discontinuation.
 
Treatment policy strategy for treatment discontinuation in the analysis using CCI [REDACTED]: CV events and deaths after the treatment discontinuation and prior to study discontinuation will be included in the analysis.
 
Hypothetical strategy for study discontinuation in the analysis using CCI [REDACTED]: Deaths after study discontinuation will not be included in the model.

Initiation of alternative therapies: 
 • Tafamidis drop-in in the vutrisiran monotherapy subgroup • CCI [REDACTED] • Prohibited medications including inotersen, commercial patisiran and vutrisiran 	
Treatment policy strategy: CV events and deaths after the initiation of these alternative therapies will be included in the analysis.
 
Initiation of tafamidis after randomization is permitted per protocol. However, a high rate of tafamidis drop-in and differential drop-in rates between two treatment arms will confound the estimate of treatment effect, which (if occurring) will be assessed by additional analyses (see Section 5.7.5).

Deaths and CV events related to COVID-19	Treatment policy strategy: CV events and deaths related to COVID-19 will be included in analysis.
Heart transplantation and LVAD placement	Composite variable strategy: Heart transplantation and LVAD placement will be treated as CV-related death.

5.7.1.2. Primary Analysis

The primary endpoint of all-cause mortality and recurrent CV events CCI [REDACTED]

CCI

The primary analysis will include events occurring during the DB period. For each patient, the Event Follow-up time will be calculated as the time from the first dose of study drug to the last Event Follow-up date (Table 3). Deaths collected after study discontinuation are not included in the analysis.

5.7.1.3. Component Analysis

The primary endpoint includes 2 components: all-cause mortality and recurrent CV events. The following will be summarized: the number of all-cause mortality (including death, heart transplant, and LVAD), the number of CV events (including CV hospitalization, indeterminate hospitalization, and urgent HF visit), the number and percentage of patients with at least one event. Vital status data after study discontinuation is not included in the above mortality component descriptive summary.

Inferential analyses for the component of all-cause mortality will include the vital status data collected after study discontinuation. The same statistical methods as that for the secondary endpoint of all-cause mortality (Section 5.7.2.2) will be used.

Inferential analyses for the component of recurrent CV events will be based on Poisson regression model with covariates including treatment, ATTR disease type, NYHA Class, age group, and baseline NT-proBNP as covariates, adjusting for the event follow-up time (i.e., including this duration as an offset). The overall population analysis will also include baseline tafamidis use and treatment-by-baseline tafamidis use interaction as covariates.

Recurrent CV events will be also analyzed using a joint frailty model (JFM) [Rondeau 2007] as a sensitivity analysis. For the JFM, the same covariates will be included for both the sub-model for recurrent CV events and the sub-model for all-cause mortality: treatment, ATTR disease type, NYHA Class, age group and baseline NT-proBNP group. The overall population analysis will also include baseline tafamidis use as a covariate. The baseline hazard functions for both recurrent CV events and all-cause mortality are approximated by piecewise constant functions. Details of the JFM methodology and implementation are provided in Appendix 9.6 .

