 - iv. If the patient has evidence of a MGUS (Section 6.5.5.1) based on serum and urine protein electrophoresis and serum free light chains, the following is required: documentation of TTR protein in cardiac tissue with immunohistochemistry or mass spectrometry; OR, documentation of TTR protein in noncardiac tissue (eg, fat pad aspirate, salivary gland, median nerve connective sheath) with immunohistochemistry or mass spectrometry AND Grade 2 or 3 cardiac uptake on technetium scintigraphy per item 2biii above.
- 3. Medical history of HF with at least 1 prior hospitalization for HF (not due to arrhythmia or a conduction system disturbance treated with a permanent pacemaker) **OR** clinical evidence of HF (with or without hospitalization) manifested by signs and symptoms of volume overload or elevated intracardiac pressures (eg, elevated jugular venous pressure, shortness of breath or signs of pulmonary congestion on x-ray or auscultation, peripheral edema) that currently requires treatment with a diuretic.
- 4. Patient meets one of the following criteria:
 - a. Tafamidis-naïve and not actively planning to commence treatment with tafamidis during the first 12 months following randomization (per exclusion criterion #7) (Note: in addition to patients who have never taken tafamidis, those who have previously been on tafamidis and have not received any tafamidis for at least 30 days before the Screening Visit will be considered tafamidis-naïve for purposes of this study); or
 - b. On tafamidis (Note: must be on-label use of commercial tafamidis per an approved cardiomyopathy indication and dose in the country of use)
- 5. Patient is clinically stable, with no CV-related hospitalizations within 6 weeks prior to randomization, as assessed by the Investigator.
- 6. Screening ccl ; in patients with permanent or persistent atrial fibrillation, Screening ccl
- 7. Able to complete ≥150 meters on the 6-MWT at Screening.

Informed Consent

9. Patient is able to understand and is willing and able to comply with the study requirements and to provide written informed consent.

10. Patient agrees to sign a separate medical records release form, where allowed by local regulations, to allow for the collection of information on vital status, cardiac transplant procedures, left-ventricular assist device placement, and hospitalizations, for the duration of the DB Period of the study (see Section 6.1).

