6.1. Screening Assessments

See the Schedule of Assessments (Table 1) for a list of Screening visit assessments.

The investigator will notify the Sponsor before screening patients to allow an assessment of the ability of the site or any new trial participant to comply with the protocol given COVID-19 pandemic limitations.

An ICF that has been approved by the appropriate Institutional Review Board (IRB)/Independent Ethics Committee (IEC) must be signed by the patient before the Screening procedures are initiated. All patients will be given a copy of the signed and dated ICF.

Due to the inclusion of all-cause mortality in the primary endpoint analysis, a Medical Records Release Form will be also required of all patients where allowed by local regulations, for the purpose of obtaining information on vital status, cardiac transplant procedures, left-ventricular assist device placement (Section 6.2.2), and hospitalizations (Section 6.2.1) from patients for the duration of the DB Period of the study. This information will be obtained by the patient's physician through contacting the patient or family or from death registries. The signing of this medical records release form is in addition to the ICF and will apply even if the patient discontinues from the study early. Also see Section 4.3.2.1 for the collection of vital status after withdrawal of consent and Section 4.3.3 for patients who are lost to follow-up.

Patients will be screened to ensure that they meet all the inclusion criteria and none of the exclusion criteria. Rescreening of patients is permitted with consultation of the Medical Monitor (see Section 6.1.2).

Patient demographic data and medical history/disease history will be obtained. Medical history will be collected during Screening (including any cardiac disorders, any eye disorders or previous ophthalmology test results, and prior medications). Any changes to medical history occurring between the screening assessment and Day 1 will be updated prior to study drug administration. Documented technetium scintigraphy and/or tissue biopsy testing for amyloidosis performed prior to study enrollment should be collected and recorded as part of medical history.

Information on prior medications, hospitalization, and procedures through 1 year prior to first dose should be collected and recorded.

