5.2. Demographics and Baseline Characteristics

Demographic and baseline disease characteristics will be summarized using the FAS.

Age at randomization, height, weight, and body mass index (BMI) will be summarized using descriptive statistics. Age group (<65; \geq 65 - <75; \geq 75), sex, race, ethnicity, and region (US; Europe; rest of world) will be summarized by presenting the frequencies and percentages of patients in each category.

The following baseline disease characteristics will be summarized by presenting the numbers and percentages of patients in each category:

- ATTR disease type [hATTR; wtATTR]
- Baseline tafamidis use [Yes; No]
- NYHA Class [I; II; III]
- NYHA Class I/II and age < 75 years [Yes; No]
- ATTR amyloidosis disease stage [1; 2; 3]
- CCI [REDACTED]
- Previous HF hospitalization [Yes; No]
- NT-proBNP (\leq 3000; >3000 ng/L)

The age at symptom onset and the time in years since hATTR or wtATTR diagnosis will be summarized, overall and by ATTR disease type, using descriptive statistics. For those who previously used tetramer stabilizers, the time from discontinuation of tetramer stabilizer to the start of study drug will be summarized using descriptive statistics. For patients in the baseline tafamidis subgroup (per the clinical database), the time from the start of tafamidis therapy to the start of study drug will be summarized using descriptive statistics.

The number and percent of patients with each ATTR disease type and with each genotype (for hATTR patients) will be summarized by country and treatment arm.

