5.3. Medical History

Medical history and prior procedures reported will be coded using the Medical Dictionary for Regulatory Activities (MedDRA), version 23.0 or newer. Unique patients who report medical history events will be summarized by MedDRA system organ class (SOC), high level term (HLT) and preferred term (PT). Other medical history data including cardiac medical history, neuropathy history, historical surgeries/procedures in the past 12 months and historical inpatient admissions or urgent healthcare visits in the past 12 months will also be summarized. Medical history data will be summarized using the FAS and presented in data listings as well.

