5.7.4. Evaluation of Subgroups

All analysis and summary results are presented by baseline tafamidis use subgroups, with vutrisiran monotherapy subgroup defined as an analysis population and background tafamidis defined as a key subgroup. Additionally, subgroup analyses will be conducted to assess the consistency of treatment effect within various subgroups defined by baseline characteristics as listed in the following table.

Subgroup	Overall population	Vutrisiran Monotherapy subgroup
Baseline tafamidis use (yes; no)	Yes	N/A
Age group (<75; ≥75)	Yes	Yes
ATTR disease type (hATTR; wtATTR)	Yes	Yes
NYHA class (I/II; III)	Yes	Yes
Baseline NT-proBNP (≤2000; >2000 ng/L)	Yes	Yes

Subgroup analyses will be performed for the composite endpoint of all-cause mortality and recurrent CV events, 6-MWT, KCCQ-OS, all-cause mortality, NYHA class, and recurrent CV events in both the overall population and vutrisiran monotherapy subgroup. The analyses will be conducted based on the subgroup data only.

- Composite endpoint of all-cause mortality and recurrent CV events:

Composite endpoint of all-cause mortality and recurrent CV events will be analyzed by LWYY model including treatment and baseline NT-proBNP as covariate. For subgroup analysis in the overall population, the model will also be stratified by baseline tafamidis use.

- Change from baseline in 6-MWT and KCCQ-OS:

Change from baseline in 6-MWT and KCCQ-OS will be analyzed by MMRM model with baseline value as a covariate, and treatment, visit, treatment-by-visit interaction as fixed effects. For subgroup analyses in the overall population, the model will also include baseline tafamidis use as a fixed factor.

- CCI [REDACTED]

- Change from baseline in NYHA class:

The binary outcome (stable or improved vs. worsened in NYHA Class at Month 30) will be analyzed by a CMH method stratified by baseline NT-proBNP. For subgroup analysis in the overall population, the model will also be stratified by baseline tafamidis use.

- Recurrent CV events:

The frequency of CV events will be analyzed by Poisson regression including treatment and baseline NT-proBNP as covariates. For subgroup analysis in the overall population, the model will also include baseline tafamidis use as a covariate.

Forest plots will be generated to illustrate the estimated treatment effect along with 95% CI within each subgroup.

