during interval 1. The SAS PROC MCMC procedure will be used for the sampling. With the simulated samples of parameters of intercept and coefficient of covariate from the PROC MCMC Poisson regression model, the samples of CV event rates for Period 1 can be obtained for each patient with the corresponding baseline NT-proBNP within each group.

- **Stage 2: CV event time imputation for individual patients (type 3 or 4)**

The imputation will be done separately for patients who were alive and who died during the interval.

- **For patients who discontinued study in Interval 1 and were alive 18 months (either type 3 or 4):**

For each patient, the event times after study discontinuation will be generated from random samples from the exponential distribution based on the sampled CV event rate in stage 1. Event times within Interval 1 will be kept and those after 18 months will be discarded.

- **For patients who discontinued study and died in Interval 1 (type 3):**

For each patient, the event times after study discontinuation will be generated from random samples from the exponential distribution based on the sampled CV event rate in stage 1. Event times before the patient's death will be kept and those after death will be discarded.

Interval 2: 18-33/36 months

- **Stage 1: CV event rate estimation**

The CV event rates will be sampled separately from the Poisson regression model for patients who were alive or died in the interval, by treatment arm and baseline tafamidis status group. The model for sampling will include frequency of CV events during Interval 2 (through study discontinuation date) as response variable, and the observed number of CV events in Interval 1 and baseline NT-proBNP as covariates while adjusting for the event follow-up time during interval 2. With the simulated samples of parameters of intercept and coefficients of covariates from the sampling Poisson regression model, the samples of CV event rates for Period 2 can be obtained for each patient using the patient's baseline NT-proBNP and the total number of CV events during Interval 1 (observed and imputed).

- **Stage 2: CV event time imputation for individual patients (type 3 or 4)**

- **For patients who discontinued study in either Interval 1 or Interval 2 and were alive during Interval 2 (type 4):**

For patients who discontinued study in Interval 1, the entire Interval 2, i.e., from 18 months to the last survival follow-up date in the DB period, will be imputed.

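### No visible recurrent-event model adjusts for admissions and urgent visits in the year before first dose, although these are collected and could modestly improve precision at little cost

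*SAP*

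**What the plan says.** **What is collected.** Protocol 6.1: "Information on prior medications, hospitalization, and procedures through 1 year prior to first dose should be collected and recorded". SAP 5.3 gives it a descriptive role: "historical inpatient admissions or urgent healthcare visits in the past 12 months will also be summarized". SAP 5.2 also tabulates previous HF hospitalization as yes or no. No other use of this history is visible.

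**What the visible recurrent-event models adjust for.**
- Component Poisson model (SAP 5.7.1.3): "Poisson regression model with covariates including treatment, ATTR disease type, NYHA Class, age group, and baseline NT-proBNP as covariates", with follow-up time as an offset. The overall population adds tafamidis use and its interaction with treatment. No robust or overdispersion-adjusted variance is stated.
- Joint frailty model (SAP 5.7.1.3): "treatment, ATTR disease type, NYHA Class, age group and baseline NT-proBNP group", plus tafamidis use in the overall population.
- Subgroup models (SAP 5.7.4): "Composite endpoint of all-cause mortality and recurrent CV events will be analyzed by LWYY model including treatment and baseline NT-proBNP as covariate". The subgroup Poisson model for CV events has the same covariates. Both also account for tafamidis use in the overall population.
- Imputation of CV events (SAP 9.3): Interval 1 uses NT-proBNP alone. Interval 2 uses "the observed number of CV events in Interval 1 and baseline NT-proBNP as covariates".

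**What cannot be seen.** The model text in SAP 5.7.1.2 is blacked out, as are the end of the covariate paragraph in SAP 5.7 and the sample-size basis in SAP 2.6.

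**The concern.** Patients differ widely in their underlying rate of CV events, and in a recurrent-event comparison that spread adds directly to the variance of the treatment effect. A count of earlier events is an obvious marker of it. The SAP accepts the principle twice: the Interval 2 imputation model uses the Interval 1 count, and Appendix 9.6 introduces a frailty for heterogeneity that the covariates do not explain. The randomisation factors (tafamidis use, disease type, NYHA class with age) do not include event history. What is at stake is precision in the component and subgroup analyses. The validity of the comparison is not in question.

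**Working it through.** The documents show no event rate, effect size, overdispersion or power, so there is no plan figure to reproduce. The size has to come from stated assumptions.

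**From the documents:** 600 patients, 1:1; double-blind exposure of 33 to 36 months; and the eligibility rule of "no CV-related hospitalizations within 6 weeks prior to randomization", which leaves 46 of the 52 prior weeks informative about CV admissions.

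**Assumed:** placebo rate 0.5 events per year; rate ratio 0.75; dropout hazard 0.08 per year; NT-proBNP above 3000 ng/L in 35% of patients, with rate ratio 2; gamma frailty variance θ of 0.75 or 1.5; prior-year mean rate 0.5; fraction f of patients whose prior-year risk carries into the trial.

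**Step 1, model-based Poisson SE.** Mean follow-up is (1 − e^(−0.08×2.875))/0.08 = 2.57 years. Expected events are 300 × 0.5 × 2.57 = 385 on placebo and 0.75 × 385 = 289 on vutrisiran. The variance of the log rate ratio is A = 1/385 + 1/289 = 0.00606, so the SE is 0.078. It depends only on event totals, so a baseline covariate cannot shrink it. Simulation (800 trials per setting) gives 0.078 with and without the prior count.

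**Step 2, true variance.** Frailty adds B = 2θc/300. Here c = 1.125 × 1.077 = 1.21 allows for unequal risk (2.05/1.35² = 1.125) and unequal follow-up (7.10/2.57² = 1.077).
- θ = 0.75: B = 0.00606, SE = √(A + B) = 0.110 (simulated robust SE 0.110).
- θ = 1.5: B = 0.0121, SE = 0.135 (simulated 0.134).

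**Step 3, what the prior count removes.** Let λ = 0.5 × 46/52 = 0.442. Let k be the number of uninformative non-CV admissions per CV admission in the count. To a linear approximation, the proportional fall in variance is B/(A + B) × f²θλ/(1 + k + θλ).

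| θ | f | k = 0 | simulated, k = 0 | k = 1 | k = 3 |
|---|---|---|---|---|---|
| 0.75 | 0.5 | 3.1% | 3.1% | 1.8% | 1.0% |
| 0.75 | 1 | 12.5% | 12.9% | 7.1% | 3.8% |
| 1.5 | 0.5 | 6.6% | 6.5% | 4.2% | 2.4% |
| 1.5 | 1 | 26.6% | 24.5% | 16.6% | 9.5% |

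Example, first row, k = 0: 0.50 × 0.25 × 0.332/1.332 = 3.1%.

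With 360 patients (about 60% of 600, the monotherapy share), the simulated falls at k = 0 are 3.4%, 12.8%, 6.1% and 24.8%, in the same row order. A separate simulation with NT-proBNP adjusted and non-CV admissions mixed into the count gave about 0 to 11%, and up to about 20% with a clean CV count.

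**Step 4, uninformative history (f = 0).** At N = 600 the simulated robust SE is 0.110 before and after (θ = 0.75), and 0.134 before and 0.133 after (θ = 1.5). Across all settings the mean log rate ratio moves by at most 0.003.

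**Step 5, the Poisson SE under no effect, θ = 1.5.** The model SE is √(2/385) = 0.072. The true SE is √(0.0052 + 0.0121) = 0.132. A nominal 5% test rejects when |Z| exceeds 1.96 × 0.072/0.132 = 1.07, which is about 28% of the time. Simulation gives about 0.29, and about the same with the covariate added.

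**The case against.** **The alpha-bearing analysis is hidden.** The multiplicity procedure (SAP 4.6) covers the primary composite, 6-MWT, KCCQ-OS, all-cause mortality and NYHA class. Its only recurrent-event test is the primary LWYY model, whose covariates cannot be read. Every visible model discussed here is a component, sensitivity or subgroup analysis. This stands. A reader might infer that the primary analysis loses power. The documents do not support that: prior events may already be in the model, and no correlation, rate or power is shown.

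**The history is only a proxy.** A reader might take it as the baseline value of the outcome. The outcome is CEC-adjudicated: non-elective CV hospitalizations and urgent HF visits. The history covers admissions and urgent visits generally, is not stated to be adjudicated, and by eligibility has no CV hospitalizations in its last 6 weeks. Some prior-year windows may overlap the pandemic, when Protocol 1.5 expected fewer admissions. This also stands, and is why the mixed-count range is the realistic one. The Interval 2 analogy is weaker for the same reason, since it uses on-study counts.

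**The quoted model would report the same interval.** Correct as written (Step 1). The gain appears only with a robust variance, as in LWYY, or plausibly in the frailty model, for which no gain was computed.

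**Some imputation cells are too sparse.** SAP 9.3 fits separately by death status, arm and tafamidis group. With about 40% of patients on tafamidis there are 120 per arm. At an assumed death rate of 0.08 per year, 1 − e^(−0.12) = 11% die by 18 months, or about 14 patients per cell. That is too few for another coefficient, so the remedy excludes those cells.

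**Randomisation makes the unadjusted comparison valid.** Agreed. No bias is claimed.

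**Conclusion.** The omission is real in every recurrent-event model that can be read, and its consequence is modest. Adjustment would lower the robust variance by about 0 to 10% with a mixed admissions count. In the table that is exceeded only when risk is fully persistent, frailty variance is 1.5 and non-CV admissions are about as frequent as CV ones. With a clean CV count and fully persistent risk the fall reaches about 20 to 25%. If the history carries no information, essentially nothing is lost. All of this rests on assumed rates, heterogeneity and persistence, because the plan's own figures are blacked out. No claim is made about the primary LWYY model or its power. The missing variance statement for the Poisson model matters more than the covariate: with strong overdispersion its nominal 5% test could reject nearly 30% of the time, and the covariate alone would not cure that.

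**What to change.** Before unblinding:
- Prespecify log(1 + count of events in the 12 months before first dose). Count CV or HF admissions and urgent visits if they can be identified; otherwise use previous HF hospitalization yes/no. Add a simple rule for missing history.
- Put it in the Poisson and joint frailty models of SAP 5.7.1.3, in the LWYY and Poisson subgroup models of SAP 5.7.4 where event counts allow, and in the primary LWYY model if it is not already there.
- State a robust (sandwich) or overdispersion-adjusted variance for the Poisson model.
- In SAP 9.3, leave the covariate out of the cells for patients who died.

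The cost is one covariate, a coding rule and a variance option. No new data are needed. If CV or HF admissions must be picked out of the history, that requires a blinded classification step.
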